**5.4.4 Final Study Visit (Study Visit 3)**

At 180 (+/- 14) days post discharge, all participants will have a routine clinic visit. The visit will include an assessment of current medication use and doses, physical examination including heart rate assessment (by exam and 1 ECG), and systolic blood pressure. The final dose of ivabradine prior to the visit will be recorded. Participants never initiated on or eligible for ivabradine will also be recorded. The study investigators or designee will assess quality of life (KCCQ and PGA).

Using the study schedule of assessments, provider-determined heart rate will be assessed at the following time points: baseline, post-discharge clinical follow-up visit (within 7-14

PRIME-HF

---

days of hospital discharge), week 6, and day 180. Patient quality of life assessment will be assessed at the following time points: baseline, post-discharge clinical follow-up visit (within 7-14 days of hospital discharge), week 6, and day 180.

PRIME-HF

---

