### **13.5 Handling of Missing Data**

All efforts will be made to make sure all data needed for the analyses outlined in the SAP are complete. However, it is possible that some data will be missing. Missing data is a common problem in clinical research. It reduces statistical power (the probability that the test will reject the null hypothesis when it is false) and results in biased parameter estimates (Kang, 2013). Outcomes for participants who do not provide data during the 180 day visit will be imputed as failures. Missing heart rate, PGA and KCCQ values will be imputed for the final (180 day) visit using multiple imputation technique if more than 10% of the measures are missing.

It is expected that missing 180 day visit values constitute > 10% of the secondary endpoints (Heart rate, KCCQ and PGA). Thus, multiple imputation (MI) will be performed and presented for the ITT and Treated populations, respectively.

Imputation will be conducted using PROC MI and imputed data analyzed with PROC MIANALYZE in SAS 9.4.

The following variables shall be used in the imputation:

AGE, SEX, RACE, ETHNICITY, WEIGHT, NYHA class, LVEF, and baseline value of the imputed variable) – For NYHA class, WEIGHT and LVEF, baseline values will be used.

RACE shall be recoded to: White, Black and Others (combining American Indian, other, and mixed - as they are of very low frequency)

Results of the imputation shall be presented as the primary result of the secondary endpoints. A total of 25 imputations will be conducted for each imputed value.

Sensitivity analyses will be conducted by analyzing these endpoints with and without imputation.

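### The imputation behind the headline heart-rate, KCCQ and PGA results uses baseline variables only; this can bias arm means, and the treatment difference if early course or dropout differs by arm

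*SAP*

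**What the plan says.** SAP 13.5 fixes the variables for the multiple imputation as "AGE, SEX, RACE, ETHNICITY, WEIGHT, NYHA class, LVEF, and baseline value of the imputed variable", and adds: "For NYHA class, WEIGHT and LVEF, baseline values will be used". Every variable is demographic or baseline. Randomised arm and baseline beta-blocker use, both terms in the SAP 9.2 models, are not listed, and imputation by arm is not mentioned.

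The same section expects more than 10% of day-180 values to be missing, and states: "Results of the imputation shall be presented as the primary result of the secondary endpoints". The named check is: "Sensitivity analyses will be conducted by analyzing these endpoints with and without imputation".

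Protocol 5.4.4 says "Patient quality of life assessment will be assessed at the following time points: baseline, post-discharge clinical follow-up visit", then week 6 and day 180. For heart rate it says "provider-determined heart rate will be assessed at the following time points: baseline, post-discharge clinical follow-up visit", again followed by week 6 and day 180. The schedule in Protocol 5.5 agrees. ECG is scheduled only at baseline and day 180, so interim heart rates are vital-sign readings, whereas the endpoint uses ECG first (SAP 5.2 footnote, SAP 13.1).

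**The concern.** Week-6 and day 7-14 scores are likely to be the trial's closest information on where a participant who later drops out was heading. Imputing from baseline alone assumes that, given baseline, missingness is unrelated to early post-discharge course. That is a strong assumption after a heart-failure admission. If participants doing badly at week 6 tend to leave, they are imputed as typical for their baseline profile, and the reported arm means are too favourable. The check with and without imputation cannot reveal this, because neither version uses interim values. The imputation is also run in the treated population, which SAP 2.4 defines by receiving ivabradine at the week 6 visit. Those participants were by definition followed to week 6, yet their week-6 scores are left out too.

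**Working it through.** **The plan's own figure.** Protocol 10.2 gives KCCQ SD 16, a 5-point difference, N=450, about 8% missing and two-sided 0.05. Per arm, 450 × 0.92 / 2 = 207. SE = 16 × √(2/207) = 1.57, and power = Φ(5/1.57 − 1.96) = 0.889. The stated power of approximately 90% is reproduced.

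**Precision at actual enrolment.** SAP 2.3 gives 104 participants. With 20% missing (assumed), 104 × 0.80 / 2 = 41.6 per arm. Adjusting for a baseline correlated 0.4 with day 180 (assumed), SE = 16 × √(2/41.6) × √(1 − 0.4²) = 3.2 points. Without baseline adjustment, power for 5 points is about 36% with no missing data and 30% with 20% missing.

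**Simulation.** At least 1,000,000 participants per scenario; the difference comes from a linear model on arm and baseline. From the documents: SD 16 and the 5-point difference. Assumed: normal scores; correlations of 0.4 (baseline/day 180), 0.5 (baseline/week 6) and 0.7 (week 6/day 180); 20-30% missing; log-odds of dropout rising by 1 or 2 per SD fall in the week-6 score.

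Results with arm in the imputation model but no interim values:

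| Scenario | Missing | Slope | Bias in arm means | Difference (true) |
|---|---|---|---|---|
| Same early course, no effect | 20% | 1 | +1.4 in both | 0.0 (0) |
| Same early course, no effect | 30% | 2 | +3.2 in both | 0.0 (0) |
| Effect appears only after week 6 | 20% | 1 | about +1.4 in both | 5.0 (5) |
| Effect of 5 already at week 6 | 20% | 1 | +1.3 to +1.6 | 4.7 (5) |
| Effect of 5 already at week 6 | 20% | 2 | not shown | 4.38 (5) |
| Effect of 5 already at week 6 | 30% | 2 | up to +3.6 in one arm | 4.22 (5) |
| Effect of 8 already at week 6 | 25% | 1 | not shown | 4.4 to 4.5 (5) |
| Effect of 8 already at week 6 | 25% | 2 | not shown | 3.85 (5) |
| Dropout follows week 6 in usual care only, no effect | about 20% | 1 | +1.5 and 0.0 | −1.5 (0) |
| Same link, 31% v 13% missing, no effect | as stated | 1 | +2.2 and +1.0 | −1.2 (0) |

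The loss in the difference runs from 5 − 4.7 = 0.3 to 5 − 3.85 = 1.15 points, or 0.1 to 0.4 of the 3.2-point SE. The spurious 1.5 points is about 0.5 SE. An extreme case, with dropout linked to week 6 in opposite directions in the two arms, gives −3.1 when the truth is 0, about one SE.

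**What removes the bias.** With arm and the interim values both in the model, arm means and difference return to the truth within simulation error in every scenario. Interim values without arm do not achieve this:
- Effect only after week 6, 20% missing: 4.0 of 5, no better than the SAP list as written.
- Effect of 5 already at week 6: 4.5 to 4.7 of 5.

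The reason is that imputing without arm pulls the imputed values in both arms together. Even under completely random dropout, the difference shrinks by about the missing fraction: 5 × (1 − 0.20) = 4.0, which the simulation also gives.

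**The case against.** A reader might infer that dropout driven by early course always biases the treatment difference. The documents do not support that. If the arms share the same early course, dropout rate and dropout mechanism, the errors in the two arm means cancel. The documents give no dropout by arm. An open-label comparison makes unequal dropout possible but does not establish it.

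Other points on the plan's side:
- **Less data may be missing than feared.** Final-visit activities are performed at discontinuation (Protocol 7.4, 8.10), and clinic data within 60 days of the window are used (SAP 13.1). This reduces the problem, but SAP 13.5 still expects more than 10% missing.
- **Heart rate is partly covered.** SAP 5.2 and Appendix 2 plan a mixed model over all visits that tests treatment at day 180. It is not the endpoint analysis and assumes a linear time trend. Appendix 2 speaks generally of measures taken at more than two time points, which could be read to include KCCQ and PGA. However, SAP 13.2 keeps the general linear model for secondary change endpoints, and no mixed model is named for those two.
- **The sizes are assumption-driven.** Correlations, dropout slope and missing share are not in the documents, and all figures are for a KCCQ-type score. Nothing was computed for heart rate or PGA.
- **The effect is small against the noise.** With an SE near 3.2 points, a bias of about a point would seldom change a conclusion.

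All of these stand as limits on size. None supplies the interim values that the headline imputation leaves out.

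**Conclusion.** The point holds in a conditional form. The listed imputation model is baseline-only, closer measurements exist, and the imputed result is the headline. If dropout follows early course, both arm means are biased, illustratively by 1.4 to 3.2 points against the 5-point difference in Protocol 10.2. The difference is biased only if early course, dropout rates or their link differ by arm. With arm in the model, that means 0.3 to 1.2 points of a true 5 when treatment already moves the week-6 score, or about 1.5 spurious points when dropout follows early course in one arm only. Both are below sampling error at n=104. All sizes rest on the assumed correlations, slopes and missing shares. This is an inexpensive improvement to secondary endpoints; it does not invalidate them, and it leaves the primary endpoint untouched. The absence of arm from the list is a separate and more certain source of shrinkage, and it has to be corrected in the same edit for the interim values to have their full effect.

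**What to change.** In SAP 13.5, add to the PROC MI model:
- the visit-1 and visit-2 values of the variable being imputed (vital-sign readings for heart rate);
- randomised arm, or impute separately by arm;
- baseline beta-blocker use.

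Use fully conditional specification for partly missing interim values. Keep the 25 imputations and the SAP 9.2 analysis models. If arm was always meant to be in the model, say so.

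The cost is a few lines of text and code, and no new data. The downside is a few more predictors in 104 participants, which can be offset by dropping weak ones such as ethnicity. SAP 1 provides the supplement and amendment routes. Addendum 2 to SAP version 2.0 records a decision taken after database lock and unblinding. If this change comes after that stage, label it post hoc and report it beside the specified analysis.

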### **13.6 Exploratory Analyses**

All analyses that are not specified as the primary or the secondary or tertiary endpoints are to be considered exploratory. All exploratory analyses are considered descriptive and are used as further hypothesis generating endeavors and no p-values will be calculated.

### **13.7 Multiple Comparisons**

No multiple comparison adjustment will be used implemented in this study.

## **15 APPENDICES**

## Appendix 1

### Data Sources for Endpoints

#### 1. Ivabradine use

a) Ivabradine use (1/0) at 180 days comes from either the current medications data (CM) or the ivabradine usage data (DRG).

If CM.CMIVA=1 and VISITID=50 or DRG.DRIVA=1 and VISITID=50. If missing then it is imputed to 0. (Note: analysis will also be done without imputation).

b) Ivabradine dose change from baseline to 180 days

Ivabradine use and dose at baseline comes from the ivabradine initiation in hospital (EXH) data EXH.EXRECH (use) and EXH.EXLDH (dose) EXH.EXRECH (use) and EXH.EXLDH (dose) (VISITID=10) and ivabradine obtaining the first time (outpatient) (EX) EX.EXREC and EX.EXPDOS (VISITID=60 study wide to be merged in)

For other time points use the ivabradine usage data DRG.DRIVA (use) DRG.DRDSG (dose). Missing doses will be imputed to 0. (Note: analysis will also be done without imputation).

Dose change from baseline to 180 days = EXH.EXLDH, EX.EXDOS (VISITID=10)-DRG.DRDSG (where VISITID=50)

c) Proportion with any initiation

If participant received ivabradine at any time during the visits

If EXH.EXRECH=1 or EX.EXREC=1 or CM.CMIVA=1 or DRG.DRIVA=1 at any visit then ANYIVA=1 else ANYIVA=0; (Note: No imputation of missing ivabradine use occurs for this derivation)

d) Proportion on maximum dose at 180 days

Use ivabradine usage data

If DRG.DRSG =15 (mg) and VISITID=50 then on ivabradine maximum dose=1; else if DRG.DRSG not missing on ivabradine maximum dose=0.

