### **5.2 Baseline Evaluations**

At the baseline visit and the time of randomization (prior to administration of ivabradine), all study participants will undergo the following:

- History and physical examination
- Baseline heart rate assessment via ECG (if ECG not already obtained in screening)
- KCCQ and PGA

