### **5.3 Treatment Intervention**

Participants randomized to pre-discharge initiation of ivabradine should receive the first dose of medication prior to discharge if possible. If ivabradine is administered and then discharge is delayed, participants should continue on open-label ivabradine until hospital discharge. Participants should then receive a prescription for outpatient ivabradine. Study drug will not be provided as part of the study. If the patient is randomized to pre-discharge initiation, the study team and/or inpatient care team (e.g., providers and care coordinator) should initiate the process to acquire outpatient medication, explore patient costs and consider support options for the patient. If the patient is not able to pay for the medication, they will continue in the study and will enter a registry of ivabradine-eligible

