## **6 MEDICATIONS**

A summary of medication usage will be presented by randomization arm over time. The summary will show the frequencies and percentages of participants using the medications. Beta-blocker and Ivabradine doses taken will be summarized by randomization arm. Beta-blocker dose descriptive summary will be presented in Carvedilol equivalent unit. Reasons for not taking beta-blocker will be summarized as frequencies and percentages by randomization arm over time. Dose data will be analyzed using the mixed model approach described in Appendix 2. A data listing of the medications will be presented.

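### SAP Appendix 1, item 1(b) takes the baseline ivabradine dose from records made after randomisation, so the derived dose change depends on the assigned arm and can point the opposite way to the day-180 doses

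*SAP*

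**What the plan says.** Protocol 5.2 fixes the timing of baseline: "At the baseline visit and the time of randomization (prior to administration of ivabradine), all study participants will undergo the following". The in-hospital dose comes later and belongs to one arm only (Protocol 5.3): "Participants randomized to pre-discharge initiation of ivabradine should receive the first dose of medication prior to discharge if possible". In usual care, ivabradine may be started after discharge at the physician's discretion (Protocol 4.5).

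SAP Appendix 1, item 1(b), derives a change in ivabradine dose. Its source statement is "Ivabradine use and dose at baseline comes from the ivabradine initiation in hospital (EXH) data". To this it adds the form for the first outpatient supply: "EX.EXREC and EX.EXPDOS (VISITID=60 study wide to be merged in". The formula is "Dose change from baseline to 180 days = EXH.EXLDH, EX.EXDOS (VISITID=10)-DRG.DRDSG (where VISITID=50", and the item adds "Missing doses will be imputed to 0", with a parallel analysis without imputation. Addendum 2 later reverses the sign of all change scores to day 180 minus baseline.

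SAP section 6 adds: "Dose data will be analyzed using the mixed model approach described in Appendix 2". The listed dose endpoint, in SAP 2.5.3 and 9.3, is the mean dose at day 180, not a change from baseline.

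**The concern.** A baseline value should be fixed before the assigned strategy can affect it. Here the strategy produces it. A pre-discharge participant dosed in hospital carries a non-zero baseline because of the assignment. If that participant cannot then obtain the drug, the change is negative. A usual-care participant who never starts has change 0 if the zero rule covers that record. One who starts later has a baseline of either 0 or the first outpatient dose, depending on how item 1(b) is read.

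The SAP does not treat beta-blockers this way. Their baseline use and dose come from the current-medication panel at visit 10 (Appendix 1, item 5).

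At stake is the reading of any dose-change table. In a trial of early initiation, it could suggest that pre-discharge initiation lowers dose relative to usual care while the day-180 doses show the reverse. The same record may also become the first point of the dose series in the section 6 mixed model, because item 1(b) assigns the ivabradine usage form to the other time points.

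**Working it through.** **Inputs.** From the documents: day-180 use of 50% (pre-discharge) and 35% (usual care), Protocol 10.2; starting dose 5 mg twice daily, so 10 mg/day, Protocol 4.5; maximum 15 mg/day, which Appendix 1, item 1(d), records as a daily total. Assumed: every dose carried as baseline is 10 mg/day; users in both arms have the same mean day-180 dose d, taken as 10, 12.5 or 15 mg/day; non-users count as 0.

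**The plan's own figure.** The documents give no figure for dose change. The rates used here are those behind the sample size, which reproduces. For 35% v 50%, two-sided 0.05, 85% power and a continuity-corrected chi-square test, 207 per arm are needed, or 414 in total; 414 / 0.92 = 450.

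**Formula.** Let s1 and s0 be the shares carrying a non-zero baseline dose under item 1(b) in the pre-discharge and usual-care arms. With the Addendum 2 sign:

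- Change, pre-discharge = 0.50d - 10 x s1
- Change, usual care = 0.35d - 10 x s0
- Contrast in change = 0.15d - 10 x (s1 - s0)
- Contrast in day-180 dose = 0.15d

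The contrast in change turns negative when s1 - s0 exceeds 0.015d:

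- d = 10: 15 points
- d = 12.5: 18.75 points
- d = 15: 22.5 points

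**Two readings of item 1(b).** Reading A: only the in-hospital visit-10 record is baseline, so s0 = 0 and s1 is the share dosed in hospital. Reading B: the first outpatient dose is merged in, so s0 is the share of usual care ever started, 0.35/q, where q is the share of those starters still on drug at day 180.

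| Reading | d | s1 v s0 | Change, pre-discharge | Change, usual care | Contrast in change | Day-180 contrast |
|---|---|---|---|---|---|---|
| A | 10 | 100% v 0 | 5.0 - 10.0 = -5.0 | +3.5 | -8.5 | +1.5 |
| A | 15 | 60% v 0 | 7.5 - 6.0 = +1.5 | +5.25 | -3.75 | +2.25 |
| A | 15 | 20% v 0 | 7.5 - 2.0 = +5.5 | +5.25 | +0.25 | +2.25 |
| B, q = 1 | 12.5 | 100% v 35% | 6.25 - 10.0 = -3.75 | 4.375 - 3.5 = +0.875 | -4.625 | +1.875 |
| B, q = 0.8 | 10 | 100% v 43.75% | -5.0 | 3.5 - 4.375 = -0.875 | -4.125 | +1.5 |
| B, q = 0.6 | 15 | 80% v 58.3% | 7.5 - 8.0 = -0.5 | 5.25 - 5.83 = -0.58 | +0.08 | +2.25 |

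All doses are in mg/day. The contrast reverses in four of these rows and not in the other two.

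**Sensitivity to equal d.** If pre-discharge users averaged 15 and usual-care users 10, the day-180 contrast would be 0.50 x 15 - 0.35 x 10 = 4.0, and reversal would need a difference of 40 points.

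**Internal consistency.** The source sentence names EXPDOS at visit 60, while the formula names EXDOS at visit 10. The text cannot settle whether Reading A or Reading B is meant.

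**The case against.** The strongest reply is that nothing important rests on this derivation. Ivabradine dose change is not a primary, secondary or tertiary endpoint (SAP 2.5) and has no test in 9.3. The listed day-180 dose comparison does not use the baseline record, and SAP 13.6 makes unlisted analyses descriptive. This stands and limits the weight of the point. It does not remove it. The derivation sits in the appendix on data sources for endpoints, and Addendum 2 resets the sign for every change calculation, so a reported result is foreseeable.

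Three stronger readings are tempting, and the documents do not support them.

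- A reader might infer that the direction is always wrong. It is not. Protocol 5.3 asks for the in-hospital dose only where possible, and the drug is not supplied. Under Reading B with full persistence in usual care and d = 12.5, the contrast keeps the right sign while s1 is below 35 + 18.75 = 53.75%.
- A reader might expect the pre-discharge arm to fall and usual care to rise. Several rows of the table lack that pattern. Under Reading B, usual care rises only if q exceeds 10/d: 80% at d = 12.5, about 67% at d = 15, and never at d = 10.
- A reader might infer that a first outpatient dose at, say, day 100 enters the mixed model at time zero. Appendix 2 defines time as actual days from randomisation, which points the other way.

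Two further limits apply. The zero rule follows the sentence on other time points and may not cover the baseline record. Also, the in-hospital variable is labelled only as a dose, so calling it the first dose is an inference; it follows randomisation either way. The analysis without imputation is no remedy: its baseline is still post-randomisation, and it may drop participants who never started.

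**Conclusion.** The point holds in limited form. Item 1(b) labels a post-randomisation dose as baseline, contrary to Protocol 5.2, and the resulting change partly measures which arm was given drug in hospital. Under the planning rates, a 10 mg/day first dose and equal d, the contrast reverses once the arms differ by more than 15 to 22.5 points in the share carrying a baseline dose. Under Reading A, in-hospital dosing of roughly a fifth of the pre-discharge arm is about enough. Under Reading B it depends on how many usual-care participants ever start. Reversal is likely if most pre-discharge participants are dosed in hospital, but not certain.

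The mismatch in variable and visit is a separate defect that needs correcting in any case. Neither the primary endpoint nor the tertiary day-180 dose is affected. An effect on the section 6 model is possible but conditional on which records enter it. This is a correction worth making to a supporting derivation, not a threat to the trial's main conclusions.

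**What to change.** In Appendix 1, item 1(b), choose one of the following:

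- Define the baseline ivabradine dose as the dose taken before randomisation, from the baseline medication panel, and 0 if none. Prior use is not a listed exclusion, so 0 should not be assumed without that check. For participants with no prior use, change equals the day-180 dose, and the contrast becomes 0.15d: +1.5, +1.875 or +2.25 mg/day for d = 10, 12.5 or 15.
- Delete the derivation and rely on the day-180 mean dose already listed as a tertiary endpoint. Since the first option largely duplicates that endpoint, this is the simpler course.

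If change from the initiation dose is wanted, label it a post-randomisation, descriptive quantity among starters.

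In all cases, reconcile EXPDOS with EXDOS and visit 60 with visit 10. State that in-hospital and first outpatient doses enter the section 6 model only as post-randomisation values at their actual dates, as Appendix 2 already implies.

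The cost is a wording change and one derivation, with no new data collection. The appendix shows an ivabradine use flag in the medication panel but no dose field there, so any prior user's dose may need to be looked up. Addendum 2 records that the database was locked and treatment unblinded, so a change made now should be documented as such under the SAP's own amendment rule.

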### 9.3 Tertiary Analyses

1. Beta-blocker use at 180 days as assessed by the (a) proportion of participants on a beta-blocker at 180-days, (b) proportion on target dose, (c) proportion of participants who are at  $\geq 50\%$  target dose (d) the proportion discontinuing beta-blockers at 180 days and (e) the mean change in beta-blocker dose from discharge to 180 days will be compared between the randomization arms. - The mean change of beta-blocker dose will be calculated for participants who provide data at baseline and at 180 days post-discharge visits.

The proportions of participants on beta-blocker, the proportions on target dose, the proportion on at least 50% of the target dose, and the proportions discontinuing beta-blocker at 180 days will be summarized by randomization arms and tested using the Chi-square test. The change in beta-blocker dose from discharge to 180 days will be summarized and compared using the Wilcoxon rank sum test.

2. Ivabradine use at 180 days as assessed by the (a) proportion of appropriate participants with any initiation of ivabradine at 180 days, (b) the proportion of appropriate participants at the maximum dose of ivabradine at 180 day (i.e., 7.5 mg

---

 Comparing the mean change in beta-blocker dose is interpreted as comparing the distribution of dose changes between the randomization arms.

twice daily), and (c) the mean dose of ivabradine achieved at 180 days will be compared between the randomization arms.

Participants who do not provide the 180 day visit data will be coded as failures (ivabradine=0 and dosage=0.0). The mean dose of ivabradine achieved will be calculated for participants who provide data at 180 days post-discharge visit and using imputed values for the participants who do not provide 180 day visit data. As a sensitivity analysis, data will also be analyzed on observed data without imputing missing values. In addition, ivabradine dosage will be summarized for participants on ivabradine at the 180 day visit.

The proportions of appropriate participants with any initiation of ivabradine and the proportion of appropriate participants at the maximum dose of ivabradine at 180 days will be summarized as incidences by the randomization arms and tested using the Chi-Square test. The dose of ivabradine achieved at 180 days will be summarized and compared using the Wilcoxon rank sum test.

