## **8) Barriers to acquisition of ivabradine**

Barriers to the acquisition of ivabradine comes from two sources. Barriers to the first  
time acquisition of ivabradine comes from the ivabradine obtaining first time data (EX).  
Get variables EX.EXPRC, EX.EXPHRM, EX.EXAE, EX.EXLBL, EX.EXPDC,  
EX.EXDDC, EX.EXPAN, EX.EXPAS, EX.EXINS, EX.EXAPN, EX.EXAPA,  
EX.EXAPD, and EX.EXOTH (Note: VISITID=60)

For subsequent visits, the data sources is the ivabradine usage (DRG) data (Note:  
VISITID=20, 30, 40, 50). Get variables  
DRG.DRPRC, DRG.DRPHRM, DRG.DRAE, DRG.DRLBL, DRG.DRPDC,  
DRG.DRDDC, DRG.DRPAN, DRG.DRPAS, DRG.DRINS, DRG.DRAPN,  
DRG.DRAPA, DRG.DRAPD, and DR.DROTH

Note: Since all reasons that apply are checked in both data sets, create separate (1/0)  
variables for each of them.

Summarize reasons from the (1/0) variables.

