### Mixed effects model analysis of repeated measures

Data were collected over time on continuous variables such as vital signs, labs and medication doses. Since within participant observations are likely to be correlated, using an analytic method that accounts for the correlation is appropriate. The mixed effects modeling approach provides a mechanism for accounting such correlations. Further, the procedure can include data from participants with partially complete data, and unequally spaced measurements which are evident in the data collected. Thus, for measurements that are collected over more than two time points, the mixed effects modeling approach is used. The model chosen includes treatment, time, and time by treatment interactions. Time will be modeled as a continuous variable which is the time to actual measurement expressed as days from randomization (DAYS). The model will assume a linear relationship between response measure and time, and allow for the intercept and slope of the linear model to differ by treatment group

The model posited is:

$$\text{Response (MEASURE)} = \text{intercept} + \text{Treatment (TRT)} + \text{Time (DAYS)} + \text{Treatment (TRT)*Time (DAYS)}$$

However, the test for treatment effect in the above model tests effects at baseline which is of little value.

It is more valuable to test treatment effects after the intervention had time to affect outcomes. Accordingly, the 180 day time point is recoded to time zero as follows.

$$\text{RDAYS} = \text{DAYS} - 180$$

And fit the model:

$$\text{Response (MEASURE)} = \text{intercept} + \text{Treatment (TRT)} + \text{Time (RDAYS)} + \text{Treatment (TRT)*Time (RDAYS)}$$

The within-patient residual covariance matrix will be modeled using a compound symmetry structure, which assumes equal correlation between measurement times within a patient. The residual covariance matrix will be assumed to be the same in the two treatment groups.

Tests of fixed effects in the model will be calculated using the Kenward-Roger method for estimating denominator degrees of freedom.

To fit the model the mixed effects model below is used;

```
proc mixed data=data;
Class TRT SUBNUM RDAYSC; *RDAYSC is defined to be equal to RDAYSC;
Model MEASURE= TRT RDAYSC TRT*RDAYSC / ddfm=KR;
Repeated RDAYSC /sub=SUBNUM TYPE=CS; /Compound symmetry covariance structure/
Run;
```

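### SAP Appendix 1 item 1(b) sets any missing post-baseline ivabradine dose to 0 mg, even for a recorded user, which is wider than SAP 9.3 and at odds with item 1(d)

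*SAP*

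**What the plan says.** **Appendix 1, item 1(b), dose.** For time points after baseline: "For other time points use the ivabradine usage data DRG.DRIVA (use) DRG.DRDSG (dose". The next sentence is "Missing doses will be imputed to 0", followed by "Note: analysis will also be done without imputation". No condition is placed on recorded use or on why the dose is missing.

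**Appendix 1, item 1(a), use.** "Ivabradine use (1/0) at 180 days comes from either the current medications data (CM) or the ivabradine usage data (DRG". Use therefore has two sources and post-baseline dose has one.

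**SAP 9.3, item 2.** "Participants who do not provide the 180 day visit data will be coded as failures (ivabradine=0 and dosage=0.0". The mean dose at day 180 uses imputed values for those participants and observed values for everyone else. An observed-data sensitivity analysis and a separate dose summary among day-180 users are also planned.

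**SAP 13.5.** Failure imputation is again tied to absent day-180 visit data.

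**Appendix 1, items 1(c) and 1(d).** Any initiation is derived without imputation. Maximum dose is coded only where the dose field is not missing. (The field name is spelled slightly differently in 1(d); I take it to be the same field.)

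**Repeated dose analysis.** SAP 6: "Dose data will be analyzed using the mixed model approach described in Appendix 2". Appendix 2 gives as one reason for the mixed model that "the procedure can include data from participants with partially complete data". Appendix 1 item 8 lists the usage form at the three interim contacts as well as at day 180.

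**The concern.** A blank dose and a dose of zero are different facts. For a recorded non-user, 0 mg is the true value. For a participant with no day-180 data, 0 mg is a stated convention that matches the primary endpoint's failure rule. For a participant recorded as taking ivabradine whose dose was not written down, 0 mg is known to be wrong, and item 1(b) assigns it.

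Two things follow. The same participant is a user in one table and takes 0 mg in another. And two programmers, one working from 9.3 and one from Appendix 1, would produce different main results for mean achieved dose, which is a named tertiary endpoint. Dose change from baseline and, possibly, the dose-over-time model and the users-only summary are exposed in the same way.

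**Working it through.** No figure in the plan is in dispute, so the check traces the rules and then illustrates the size.

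**1. Rule trace at day 180**

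| Participant | Use, 1(a) | Dose, 9.3 | Dose, 1(b) | Maximum dose, 1(d) |
|---|---|---|---|---|
| Recorded non-user, dose blank | 0 | not addressed | 0 | missing |
| No day-180 data | 0 (imputed) | 0 | 0 | missing on the raw field |
| Recorded user, dose blank | 1 | no imputation stated | **0** | missing |

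The rules conflict to a participant's harm only in the last row. It can arise from a user recorded on the medication list alone, or from a usage form with use ticked and dose empty.

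**2. Does the planned unimputed run settle it?** Item 1(b) gives two runs: every missing dose set to 0, or none. The main analysis in 9.3 sets 0 only where day-180 visit data are absent. If even one recorded user has a blank dose, neither run reproduces it.

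**3. One record.** Assume the 104 enrolled split evenly (52 per arm), 50% use (the planning rate for the pre-discharge arm) and 10 mg/day in users. The dose is my assumption. Users: 0.50 × 52 = 26; total dose 260 mg/day; true mean 260/52 = 5.00. With one user's dose blank:
- zero-filled: 250/52 = 4.81, a shift of 0.19;
- left missing: 250/51 = 4.90, a shift of 0.10.

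If that user was also on 10 mg/day at baseline, zero-filling records a change of 10 mg/day where there was none.

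**4. By share of users with a blank dose.** Let p be the use rate (0.50 and 0.35, SAP 2.3), D = 10 mg/day (assumed) and m the share of users with a blank dose (assumed, at random among users). Absent day-180 visits are left out so that only the disputed case is measured.
- True arm mean: pD, giving 5.00 and 3.50, difference 1.50.
- Zero-filled: pD(1 − m).
- Left missing: pD(1 − m)/(1 − pm).

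| m, pre-discharge / usual care | Difference, zero-filled | Difference, left missing |
|---|---|---|
| 5% / 5% | 4.75 − 3.325 = 1.43 | 4.872 − 3.384 = 1.49 |
| 10% / 10% | 4.50 − 3.15 = 1.35 | 4.737 − 3.264 = 1.47 |
| 20% / 20% | 4.00 − 2.80 = 1.20 | 4.444 − 3.011 = 1.43 |
| 10% / 0% | 4.50 − 3.50 = 1.00 | 4.737 − 3.50 = 1.24 |
| 20% / 0% | 4.00 − 3.50 = 0.50 | 4.444 − 3.50 = 0.94 |
| 0% / 10% | 5.00 − 3.15 = 1.85 | 5.00 − 3.264 = 1.74 |
| 0% / 20% | 5.00 − 2.80 = 2.20 | 5.00 − 3.011 = 1.99 |

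Leaving the dose missing is better in every row but not unbiased, because a user leaves the calculation while non-users stay at 0. The share of an arm's bias that remains is (1 − p)/(1 − pm). At m = 10% this is 0.50/0.95 = 53% in the pre-discharge arm and 0.65/0.965 = 67% in usual care.

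**5. A blank dose at an interim visit.** Take one steady 10 mg/day user seen at about days 10, 42, 90 and 180 (assumed times). The mean time is 80.5 and the sum of squared deviations 16,443. Zero-filling the dose at time t gives a mean of 7.5, a slope of −10(t − 80.5)/16,443, and a fitted day-180 value of 7.5 + 99.5 × slope:
- t = 10: 7.5 + 4.27 = 11.8;
- t = 42: 7.5 + 2.33 = 9.8;
- t = 90: 7.5 − 0.57 = 6.9.

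Leaving the dose missing gives 10. Day 180 is where Appendix 2 tests the treatment effect. This is one person's line; in the model it is diluted across all participants, and it arises only if zero-filled doses are passed to the model.

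**The case against.** The strongest reply is that this is a wording mismatch in a derivation appendix. Item 1(b) is headed as change from baseline to day 180, and its formula uses only those two visits. SAP 9.3 and 13.5 state the narrower rule in the body of the plan, an unimputed analysis is promised alongside, and nothing outside dose is touched. Day-180 dose is tested by a Wilcoxon rank sum test, so a shift in the mean is not the tested quantity. All of that stands and limits the weight of the point. It does not remove it. The sentence is unconditional, the unimputed run is not 9.3's main analysis, and in a rank test a user set to 0 is tied with the non-users.

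Three stronger readings are tempting, and the documents do not support them.

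- **A missed interim contact is entered as 0 mg, as a false stop and restart.** Appendix 2 models time as the day of actual measurement. A contact that did not happen has no such day, and nothing tells the programmer to create a row for it. SAP 13.1 also admits clinic data within 60 days of a missed window. Only a blank dose on an existing record is plainly reached.
- **The participant is analysed as off the drug.** Items 1(a) and 1(c) keep a recorded user as a user, and 1(d) leaves the dose missing. Only the imputed dose variable is affected.
- **The bias follows overall missingness, such as the 8% allowed for in protocol 10.2.** That allowance is for missing primary endpoint data. Participants without day-180 data get 0 mg under 9.3 by design and would still do so after the change.

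Whether an imputed zero enters the users-only summary is also open: 9.3 does not say which dose values that summary uses.

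**Conclusion.** The point holds, with low impact. As written, item 1(b) gives a recorded day-180 user with a blank dose a value known to be wrong in the imputed mean-dose and dose-change analyses. It conflicts with 9.3 and 13.5 on scope and with 1(d) on how the same blank field is treated. A recorded user's blank dose at an interim visit is affected too, if zero-filled doses feed the mixed model, which does not need them.

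The primary endpoint, any initiation and maximum dose (read on the raw field) are unaffected. The size cannot be stated, because the documents give no rate of blank doses among users. It is probably small: about 0.19 mg/day on an arm mean per record, under the assumptions above. The table shows that an imbalance between arms matters more than the overall rate, but every missing-dose rate in it, and the 10 mg/day, is assumed. A reader might go on to infer inflated standard errors in the dose model; nothing in the documents quantifies that, and I do not claim it.

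**What to change.** Replace the zero-fill sentence in item 1(b) with a rule that:
- sets dose to 0 only when non-use is recorded at that visit and no source used in 1(a) shows use, or, at day 180, when no visit data exist (the 9.3 rule);
- leaves dose missing for a recorded user without a dose, at any visit;
- creates no zero records for missed interim visits, so that the mixed model uses the observed ones;
- keeps imputed zeros out of the dose summary among day-180 users.

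Also state what happens to a participant seen at day 180 with neither use nor dose recorded. SAP 9.1 and item 1(a) already code use as 0 there, so 0 mg would agree with the primary endpoint.

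The cost is a few lines of derivation text, through the supplement or amendment route in SAP 1; the unimputed run is unchanged. The downside should be stated in the plan: users without a recorded dose leave the mean-dose calculation while non-users stay at 0, so some downward bias remains, though less than with zero-filling. Report the number of such users by arm so that a reader can judge it.
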